2. LIST OF ABBREVIATIONS

ADR , Adverse Drug Reaction
AE , Adverse Event
AESI , Adverse Event of Special interest
CA , Competent Authority
CCDS , Company Core Data Sheet
CI , Confidence Interval
CML , Local Clinical Monitor
CRA , Clinical Research Associate
CRF , Case Report Form
CTCAE , Common Terminology Criteria for Adverse Events
CTP , Clinical Trial Protocol
eCRF , Electronic Case Report Form
ENCePP , European Network of Centres for Pharmacoepidemiology and Pharmacovigilance
FDA , Food and Drug Administration
GCP , Good Clinical Practice
GEP , Good Epidemiological Practice
GPP , Good Pharmacoepidemiology Practice
GVP , Good Pharmacovigilance Practices
IB , Investigator's Brochure
IEC , Independent Ethics Committee
IRB , Institutional Review Board
MAH , Marketing Authorization Holder
MedDRA , Medical Dictionary for Regulatory Activities
NIS , Non-Interventional Study
PASS , Post-Authorization Safety Study
SAE , Serious Adverse Event Adapt and complete as appropriate

Proprietary confidential information © 2021 Boehringer Ingelheim International GmbH or one or more of its affiliated companies

4. ABSTRACT

Name of company: Boehringer Ingelheim			
Name of finished medicinal product: Spiriva Respimat			
Name of active ingredient: Tiotropium			
Protocol date: 12 May 2021	Study number: 0205-0547	Version/Revision: 1.0	Version/Revision date: 12 May 2021
Title of study:	Exacerbation Risk and Health Care Resource use among patients with asthma using ICS+Tiotropium versus ICS/LABA Date: 05/12 2021 Version Number:1 [REDACTED]		
Rationale and background:	Regardless of severity level, patients with uncontrolled asthma are prone to exacerbations, increased use of systemic corticosteroids, and rescue medications. Guidelines recommend increasing the dose of ICS product or use of ICS in combination with long-acting β 2-agonists (LABA), and/or other add-on therapy such as with a long-acting muscarinic antagonist (LAMA), leukotriene receptor antagonists (LTRA), biologics or oral corticosteroids. RCTs have found similar responses in terms of lung function and exacerbations between patients on ICS/Tiotropium and ICS/LABA. ICS/LABA is very commonly used in the real world since 2003, and Tiotropium was only available in the US since 2016, so it's important we generate real world evidence data complimenting the ICS/Tiotropium RCT data as an alternative to ICS/LABA. It is important to evaluate the role of a LAMA in combination with ICS using real world data to support further treatment recommendations.		
Research question and objectives:	To conduct a comparative analysis of patients using Tiotropium in combination with Inhaled Corticosteroids (ICS) versus those that use LABA medication in combination with ICS.		
Study design:	This is a non-interventional study based on existing data. Patients will be classified into two groups: 1. ICS+Tio and 2. ICS/LABA. We will record various baseline measures, including demographics such as gender, age, and region, comorbidity level defined using Charlson Comorbidity Index (CCI), other specific comorbidities not included in the CCI, inhaled medication use, ICS dose level, control level, and other listed measures. Using propensity score matching (PSM) technique, we will develop matched cohorts of patients between the ICS+Tio and ICS/LABA groups.		
Population:	1. ICS+Tio; and 2: ICS/LABA.		

Proprietary confidential information © 2021 Boehringer Ingelheim International GmbH or one or more of its affiliated companies

Name of company: Boehringer Ingelheim			
Name of finished medicinal product: Spiriva Respimat			
Name of active ingredient: Tiotropium			
Protocol date: 12 May 2021	Study number: 0205-0547	Version/Revision: 1.0	Version/Revision date: 12 May 2021
Variables:		
The exposure variables are ICS+Tio use vs. ICS/LABA use in combination with ICS.
 
PSM
 
• Gender• Age group• Region• ICS dose level• Control level• Rescue medication use• Comorbidities included in the Charlson Comorbidity Index• ICS history (yes/no)• ICS history duration• Season of index date• Index year• Baseline all-cause resource use (presence vs. absences of hospitalizations, or ER visits, or outpatient visits)• Baseline other asthma medications (use vs. no use)• Baseline overall medication history (polypharmacy defined as number of unique medications)• Insurance type• Hypertension• Gastroesophageal reflux disease• Allergic Rhinitis• Obesity• Sinusitis• Obstructive sleep apnea• Cardiovascular disease• Diabetes• Renal failure• Arthritis• Osteoporosis• Depression• Cancer (excluding basal cell carcinoma)• Baseline pneumonia diagnosis• Diagnosis of dyspnea during baseline identified using ICD 9 786.0x and ICD 10 R06.0x	

Proprietary confidential information © 2021 Boehringer Ingelheim International GmbH or one or more of its affiliated companies

Name of company: Boehringer Ingelheim			
Name of finished medicinal product: Spiriva Respimat			
Name of active ingredient: Tiotropium			
Protocol date: 12 May 2021	Study number: 0205-0547	Version/Revision: 1.0	Version/Revision date: 12 May 2021
Variables:	
Diagnosis of alcohol dependence during baseline identified using ICD 9 303.xx, 305.0x and ICD 10 F10.xxSmoking dependence during baseline identified using ICD 9 305.1 and ICD 10 F17.xx 
Regression
 
In addition to the key independent variable of interest (ICS+TIO vs ICS/LABA group), we will include time varying medication exposure as a covariate in the regression.
		
Data sources:	We will utilize medical and pharmacy claim records from [REDACTED] medical and pharmacy claims data. This database is comprised of adjudicated claims for more than 150 million commercially insured and Medicare lives in the US.		
Study size:	There are 25,291 patients with a prescription claim for tiotropium (1.25mcg, October 2015-May 2020) identified for analysis and 1,125,657 patients with ICS/LABA prescription claims (July 2014-May 2020). After excluding patients with COPD there are 17,882 patients in the Tio group and 921,804 patients in the ICS/LABA group. Further inclusion-exclusion criteria as well as restricting the Tio group to those with concurrent ICS monotherapy, will be applied to arrive at the final sample.		

Proprietary confidential information © 2021 Boehringer Ingelheim International GmbH or one or more of its affiliated companies

Name of company: Boehringer Ingelheim			
Name of finished medicinal product: Spiriva Respimat			
Name of active ingredient: Tiotropium			
Protocol date: 12 May 2021	Study number: 0205-0547	Version/Revision: 1.0	Version/Revision date: 12 May 2021

Data analysis	Sample attrition at each step of the inclusion-exclusion criteria will be provided. We will develop the breakdown of the distribution of demographic, comorbidity, and baseline measures prior to and after the PSM (unmatched and matched cohorts). Significance of differences will be tested at $P<0.05$ for the matched cohort. Additionally, we will consider the use of standardized mean differences as noted above, in which $SMD <0.1$ indicates balance. The primary endpoint measure is time to first severe exacerbation and severe exacerbation will be defined as a hospitalization or an ER visit with a primary diagnosis of asthma. We will calculate the time in days to first exacerbation. We will conduct Cox proportional hazards modeling to estimate the risk of exacerbation and provide corresponding KM curves for the primary endpoint. Exposure to each of the study comparators (ICS+Tio and ICS/LABA) will be recorded using time-varying covariates for all primary and secondary endpoints. ICS+Tio vs. ICS/LABA will be the key independent variable and medication exposure will be a covariate included in the regression. Secondary endpoints will include time (in days) to first moderate-or-severe exacerbation defined as use of systemic corticosteroid or a hospitalization or ER visit with a primary diagnosis of asthma. Cox PH and KM curves will be conducted for this secondary end point as well. We will also calculate and compare the rate of exacerbation, proportion of patients with exacerbations after 6 months and one year among the sub-population of patients having at least 6 months and a one year of follow-up, respectively. We will report rates in patient-years to account for variable follow-up time. We will also compare the mean monthly (to account for variable follow-up time) per patient HCRU (all-cause and asthma related hospitalizations, ER visits, and outpatient visits) during the follow-up period, between the two groups. Proportions of patients with and without rescue medication use will be compared between the two groups as well.
----------------------	--

Proprietary confidential information © 2021 Boehringer Ingelheim International GmbH or one or more of its affiliated companies

5 . AMENDMENTS AND UPDATES

None

6. MILESTONES

Study design and core group alignment	Week 1-2
Data receipt, extraction, cleaning and evaluation for protocol development	Week 2
Study protocol draft	Week 4
Study protocol final	Week 6
IET/NPCC approval	Week 8/9
Descriptive statistics draft	Week 11-12
Multivariate analysis draft	Week 12-14
Final results (Excel)	Week 16-17
Study narrative report	Week 17-18

7. RATIONALE AND BACKGROUND

Asthma is associated with a significant burden on the healthcare system. More than half the population of asthma patients remains uncontrolled despite therapy, and uncontrolled asthma is associated with greater economic and health care burden (Braido et al. 2013; Peters et al. 2007). Stepwise treatment approach depending on control and severity levels has been the corner stone of asthma therapy. Regardless of severity level, patients with uncontrolled asthma are prone to exacerbations, increased use of systemic corticosteroids, rescue medications, deteriorating lung function (Chung et al. 2014), reduced quality of life, and increased health care resource use. In such cases, guidelines recommend increasing the dose of ICS product or use of ICS in combination with long-acting β 2-agonists (LABA), and/or other add-on therapy such as with a long-acting muscarinic antagonist (LAMA), leukotriene receptor antagonists (LTRA), biologics or oral corticosteroids. Treatment strategies that rely on step treatment may not always be sufficient in controlling asthma.

Given the unmet needs, other therapeutic options should be considered in this population. In investigating Tiotropium (Handihaler and Respimat) for the treatment of asthma, 6 clinical trials (found similar responses in lung function and exacerbations when comparing ICS/Tiotropium to ICS/LABA. In a randomized controlled trial of moderate asthma patients, Kerstjens et al 2015 reported a lower rate of exacerbations among patients with ICS/Tiotropium when compared to ICS/Salmeterol (ICS/LABA) however formal comparisons could not be made since the ICS/salmeterol group was included to provide a standard add-on active comparator and was not part of the inferential analysis. Kerstjens et al study concluded that “Once-daily tiotropium as add-on treatment to medium-dose inhaled corticosteroids provided significant improvements in lung function and asthma control that were similar to those recorded for twice-daily salmeterol. In summary, RCTs have found

Proprietary confidential information © 2021 Boehringer Ingelheim International GmbH or one or more of its affiliated companies
similar responses in terms of lung function and exacerbations between patients on
ICS/Tiotropium and ICS/LABA.

NHLBI recommendations: Stepwise approach for management of asthma in patients ≥ 12 years

Treatment	Intermittent Asthma		Management of Persistent Asthma in Individuals Ages 12+ Years				

8. RESEARCH QUESTION AND OBJECTIVES

To conduct a comparative analysis of patients using Tiotropium in combination with Inhaled Corticosteroids (ICS) versus those that use LABA medication in combination with ICS.

9. RESEARCH METHODS

9.1 STUDY DESIGN

1. Patients with least two asthma diagnosis (ICD 9 CM: 493.xx or ICD 10: J45-J45.999) will be included.
2. Patients will be required to be concurrently on ICS+Tiotropium (specifically Tiotropium Respimat® 1.25 mcg) or ICS/LABA.
3. Patients with least two diagnosis of COPD at any time during the study period will be excluded.
4. Patients less than 12 years of age will be excluded.
5. Patients will be required to have enrollment for at least 6 months prior to ICS+Tio or ICS/LABA use.
6. Patients on biologics within 6 months prior to ICS+Tio or ICS/LABA use will be excluded.
7. Patients with prior Tio or ICS/LABA use during the 6-month baseline period will be excluded.
8. Patients with urinary bladder obstruction, urinary retention, and glaucoma will be excluded.
9. After the PSM process, unmatched patients will be excluded.

Patients will be classified into two groups based on the exposure on the index date: 1. ICS+Tio; and 2: ICS/LABA. The date of concurrent medication initiation will be defined as the index date based on the date of the first prescription claim defining their add-on medication. We will record various baseline measures, including demographics such as gender, age, and region, comorbidity level defined using Charlson Comorbidity Index (CCI), other specific comorbidities not included in the CCI ([Table 1](#)), inhaled medication use, and control level as defined in Table 1. Additionally, we will classify patients based on their daily ICS dose levels as 'low dose ICS', 'medium dose ICS', and 'high dose ICS'. The dose levels will be assigned per GINA 2020 criteria (Global Initiative for Asthma. Global Strategy for Asthma Management and Prevention 2020). Medications that are available with only two dose level indications will be tagged as 'low' for the lower of the two dose levels, and 'high' for the highest dose level.

Proprietary confidential information © 2021 Boehringer Ingelheim International GmbH or one or more of its affiliated companies

Table 1: Baseline Parameters and Variable Definitions

Variable Name and Type	Description and Definition	Covariate Adjustment Method
Demographics	Age (5-year increments), Gender,	PSM
Region	Region (Northeast, Midwest, South, West)	PSM
CCI	Charlson Comorbidity Index score	PSM
Inhaled medication use	Identified using unique claims during the baseline period	PSM
Control Status: Not Well Controlled or Well Control	
“Not Well Controlled” if patient has any one of the following events
 
 • Prescription for OCS • Asthma-related ER • Asthma-related hospitalizations 
“Well controlled” if patient has none of the above events
 
(Ref: Stempel JACI 2005)
	PSM
ICS history	Defined by use of ICS monotherapy prior to index date	PSM
ICS history duration	Days on ICS monotherapy prior to index date	PSM
ICS dose level	Daily dose of ICS classified as low dose ICS, medium dose ICS, and high dose ICS	PSM
Season	Season of cohort entry (Summer, Spring, Fall, Winter)	PSM
Index year	Year of the index date	PSM
All-cause resource use	All-cause hospitalizations, ER visits, outpatient visits	PSM
Other asthma medications	Leukotriene modifiers	PSM
Medication history	Polypharmacy calculated based on number of unique medications	PSM
Insurance type	Identified using payer type data field	PSM
Hypertension	Identified using appropriate ICD codes. Coded as binary (yes/no) variables	PSM
Allergic rhinitis	Identified using appropriate ICD codes. Coded as binary (yes/no) variables	PSM
Sinusitis	Identified using appropriate ICD codes. Coded as binary (yes/no) variables	PSM
Obstructive sleep apnea	Identified using appropriate ICD codes. Coded as binary (yes/no) variables	PSM
Gastro-esophageal reflux disease	Identified using appropriate ICD codes. Coded as binary (yes/no) variables	PSM
Obesity	Identified using appropriate ICD codes. Coded as binary (yes/no) variables	PSM
Cardiovascular disease	Identified using appropriate ICD codes. Coded as binary (yes/no) variables	PSM
Diabetes	Identified using appropriate ICD codes. Coded as binary (yes/no) variables	PSM

Proprietary confidential information © 2021 Boehringer Ingelheim International GmbH or one or more of its affiliated companies

Table 1: Baseline Parameters and Variable Definitions (cont)

Variable Name and Type	Description and Definition	Covariate Adjustment Method
Renal failure	Identified using appropriate ICD codes. Coded as binary (yes/no) variables	PSM
Arthritis	Identified using appropriate ICD codes. Coded as binary (yes/no) variables	PSM
Depression	Identified using appropriate ICD codes. Coded as binary (yes/no) variables	PSM
Osteoporosis	Identified using appropriate ICD codes. Coded as binary (yes/no) variables	PSM
Cancer (excluding basal cell carcinoma)	Identified using appropriate ICD codes. Coded as binary (yes/no) variables	PSM
Pneumonia	Identified using appropriate ICD codes. Coded as binary (yes/no) variables	PSM
Acute bronchitis	Identified using appropriate ICD codes. Coded as binary (yes/no) variables	PSM
Dyspnea	Identified using appropriate ICD codes. Coded as binary (yes/no) variables	PSM
Alcohol dependence	Identified using appropriate ICD codes. Coded as binary (yes/no) variables	PSM
Smoking dependence	Identified using appropriate ICD codes. Coded as binary (yes/no) variables	PSM

Using propensity score matching (PSM) technique, we will develop matched cohorts of patients between the ICS+Tio and ICS/LABA groups. We will conduct 1:2 matching using nearest neighbor matching approach. Upon completion of matching, we will assess whether the cohorts are balanced by examining the statistically significant differences at $p < 0.05$. We will also assess balance by calculating standardized mean differences (SMD). An SMD < 0.1 will be considered balanced. Follow-up time will be calculated between index date and 'Censor date' which will be defined as the date of either one of the following events: 1. Date of first exacerbation, 2. Date of medication switch, 3. Discontinuation of medication (defined as date of prescription claim plus days' supply, plus 50% additional days), 4. Enrollment end date, or 5. Last date available in the dataset/End of study period. In this "new user", study design, primary analysis will be an "as-treated" analysis. In order to attribute events and outcomes to patients during the time that they are exposed to treatment (based on days-supply of prescription claims + a buffer window) as well as account for differences in inter-group adherence levels, we will use a time-varying covariate approach to classify drug exposure time for each comparator drug during follow up. This approach has been chosen to minimize bias based on potentially large differences in medication adherence rates, by only attributing outcomes to the time in which patients have medication in their possession based on days' supply as described below. For each individual study drug, we will identify and define medication exposure and non-exposure windows during the follow-up time for each medication using the date of prescription filled plus the days' supply listed on the prescription claim plus 50% additional days (to account for residual doses in canister, poor real-world adherence and latency of drug effects). For example, exposure start and stop dates

Proprietary confidential information © 2021 Boehringer Ingelheim International GmbH or one or more of its affiliated companies for a patient with a prescription claim with 30 days supply on January 1st will be January 1st and February 15th respectively (30 days' supply +15 days). We will run sensitivity analyses on the exposure window using 0% and 100% additional days. These time varying exposure covariates will be included in the Cox PH regression.

If statistical differences are found after PSM, then the study team will make a determination to either include them as covariates in the regression analysis (Cox PH), or develop interaction terms to match on, or discontinue the study. In the event of study discontinuation, partial results (all analysis leading up to and including PSM) will be provided in a final report.

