9.3.2 Endpoints

9.3.2.1 Primary endpoints

[figure not shown]
The primary endpoint measure is time to first severe exacerbation. Severe exacerbations will be defined as:

- A hospitalization with a primary diagnosis of asthma or
- An ER visit with a primary diagnosis of asthma

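### The asthma entry criterion has no time window, so a primary endpoint claim can supply the diagnosis that admits a patient; this can inflate absolute event risk and may bias the comparison

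*Combined protocol and SAP*

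**What the plan says.** The entry rule in section 9.1 is "Patients with least two asthma diagnosis (ICD 9 CM: 493.xx or ICD 10: J45-J45.999) will be included". It gives no look-back period, no link to the index date and no requirement for separate dates.

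Other items in the same list do state their timing. Criterion 5: "Patients will be required to have enrollment for at least 6 months prior to ICS+Tio or ICS/LABA use". Criterion 6: "Patients on biologics within 6 months prior to ICS+Tio or ICS/LABA use will be excluded". Criterion 7 (prior use) also refers to the six-month baseline. Criterion 3 covers the whole period: "Patients with least two diagnosis of COPD at any time during the study period will be excluded".

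The index date is set by treatment: "The date of concurrent medication initiation will be defined as the index date". Section 9.3.2.1 states "The primary endpoint measure is time to first severe exacerbation" and lists two qualifying events: "A hospitalization with a primary diagnosis of asthma or" "An ER visit with a primary diagnosis of asthma".

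The only outer bound on the asthma codes is the data extract, 2014 to 2020 (section 9.4). The matching covariates in Table 1 and section 9.3.3 do not include the number or timing of asthma diagnoses before index.

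**The concern.** Take a patient with one asthma code by the index date. If that patient has an asthma ER visit or hospitalization during follow-up, the claim is the second code and the patient enters. If not, the patient enters only if some other asthma code turns up later. Among such patients, those with the event are admitted more readily than those without it, although section 9.1 describes a new-user design in which eligibility should be settled at index.

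Two things are at stake. First, the plan reports absolute results: exacerbation proportions, rates in patient-years, and asthma-related hospital, ER and outpatient use (sections 9.3.2.2 and 9.7.1). Asthma-coded visits can admit patients, so these can be too high in both arms whatever the treatment effect. Second, if dependence on later codes differs between arms, part of the estimated hazard ratio would reflect selection.

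The planned checks would not show it. Balance tests and standardized differences cover baseline variables. The attrition table counts losses per criterion and does not show when the codes occurred. Section 9.9 does not list the problem among the limitations.

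**Working it through.** The plan gives no event rate, expected event count or effect size (section 9.5 holds feasibility counts only), so there is no figure of its own to reproduce. What follows is an illustration with assumed inputs.

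**Inputs, all assumed**
- r: true event risk, 5% (3% in steps 2 and 4).
- s: share of otherwise eligible patients with exactly one asthma code by index.
- v: chance that such a patient, without an event, gains another asthma code later.

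All other patients are taken to have two codes by index. Risk is taken as equal in both strata and independent of v.

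**Step 1. Risk among admitted one-code patients.** A fraction r + (1 − r)v is admitted, so observed risk = r / [r + (1 − r)v]. With r = 5% and v = 0.3: 0.05 / (0.05 + 0.285) = 14.9%.

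**Step 2. Risk in a whole arm.** Observed risk = r / D, with D = (1 − s) + s[r + (1 − r)v]. The inflation factor is 1/D. At r = 3%:
- s = 10%, v = 0.9: D = 0.9 + 0.1 × 0.903 = 0.9903, factor 1.01.
- s = 20%, v = 0.5: D = 0.8 + 0.2 × 0.515 = 0.903, factor 1.11.
- s = 40%, v = 0.3: D = 0.6 + 0.4 × 0.321 = 0.7284, factor 1.37.

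**Step 3. Unequal shares, true risk ratio 1.00, r = 5%.** The false ratio (larger-share arm over smaller-share arm) is D for the smaller share divided by D for the larger.

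| v | One-code stratum risk | D, s = 10% | D, s = 20% | D, s = 30% | 20% vs 10% | 30% vs 10% |
|---|---|---|---|---|---|---|
| 0.3 | 14.9% | 0.9335 | 0.8670 | 0.8005 | 1.077 | 1.166 |
| 0.5 | 9.5% | 0.9525 | 0.9050 | 0.8575 | 1.052 | 1.111 |
| 0.7 | 7.0% | 0.9715 | 0.9430 | 0.9145 | 1.030 | 1.062 |
| 0.9 | 5.5% | 0.9905 | 0.9810 | 0.9715 | 1.010 | 1.020 |

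If the larger share is in the ICS/LABA arm, tiotropium looks spuriously better (30% vs 10%: 1/1.166 = 0.86 to 1/1.020 = 0.98). If it is in the tiotropium arm, tiotropium looks worse by the same factors.

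**Step 4. Equal shares.** A true ratio of 1.00 stays 1.00. For a true ratio of 0.80 (2.4% vs 3%) with s = 20% and v = 0.5, D is 0.9024 for tiotropium and 0.9030 for ICS/LABA, and the observed ratio is 0.80 × 0.9030 / 0.9024 = 0.801.

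**Step 5. What the plan's counts can say.** The COPD step in section 9.5 removes 7,409 of 25,291 tiotropium patients (29.3%) and 203,853 of 1,125,657 ICS/LABA patients (18.1%). The source populations differ, but these counts do not measure s or v.

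**Step 6. After the fix.** If both codes must fall on or before index, no later claim admits anyone, and the selection factor is 1.00 in each arm whatever s and v are.

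**The case against.** A reader might infer that the rule inflates risk unevenly and so produces a false treatment difference. The documents do not support that. Criterion 1 is identical for both arms, and equal shares leave the ratio essentially unchanged. That tiotropium is limited to one strength with concurrent ICS monotherapy, while ICS/LABA is a broad class, makes a difference in shares plausible but does not establish one.

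Nor should one say that matching is powerless. The between-arm part of the problem runs through a baseline characteristic, the number of codes by index. Control status, ICS history and duration, resource use and index year are all matched and may correlate with it. Matching may narrow a gap, but it does not target it and does not remove the inflation within each arm.

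The ratios may also overstate the effect. Read literally, the rule counts a code from any routine visit through 2020, even after follow-up is censored, so v could be high; at 0.9 the false ratio is only 1.01 to 1.02. The calculation uses fixed risks, whereas the plan analyses as-treated time to event with time-varying exposure.

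The mechanism does not reach every endpoint component. Systemic corticosteroid use, part of the moderate-or-severe endpoint, needs no asthma code and supplies no qualifying diagnosis.

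Finally, the criterion is silent and does not expressly permit later codes; criterion 8 also has no window. A programmer might restrict to earlier codes anyway. But nothing in the plan tells them to, and following the text as written conditions entry on the outcome. These points limit the claim about the comparison and leave the defect in the criterion standing.

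**Conclusion.** The concern holds as a defect in the entry rule with a conditional effect on the comparison. As written, a primary endpoint claim can complete eligibility. Wherever patients have only one code by index and some never gain another without an event, absolute severe-exacerbation risk is inflated: by a factor of 1.01 to 1.37 at an assumed 3% risk, with one-code shares of 10% to 40% and v from 0.3 to 0.9. Exacerbation rates and asthma-related resource use are exposed in the same way.

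The hazard ratio may be biased if dependence on post-index codes differs between arms after matching. Neither size nor direction can be derived from the documents. The range of 1.01 to 1.17 is illustrative and rests on assumed shares of 10% against 20% or 30%, a 5% risk and v from 0.3 to 0.9. The correction should be made before the cohort is built.

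**What to change.** Reword criterion 1 to require at least two asthma diagnoses on separate dates, both on or before the index date, and state that later codes do not count toward entry. Report by arm how many patients qualify only through post-index codes. Keep the current rule as a labelled sensitivity analysis.

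The cost is one line of protocol text and one change in the cohort code, with no new data. Some patients with a single earlier code will be lost; how many cannot be derived from the documents. The loss is mainly a concern in the tiotropium arm, which has 17,882 patients before the ICS restriction and remaining criteria, against 921,804 for ICS/LABA (921,804 / 17,882 = 51.5).

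The new rule has a weakness of its own: look-back length varies with index date. The extract starts in 2014, ICS/LABA claims in July 2014 and tiotropium 1.25 mcg claims in October 2015, so the earliest ICS/LABA patients have less time to accrue two codes. Matching on index year addresses this only partly. A sensitivity analysis with a fixed look-back is advisable, for example the six months before index that criterion 5 guarantees.

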9.3.3 Covariates

The covariates included in the PSM will be

- Gender
- Age group
- Region
- ICS dose level
- Control level
- Rescue medication use
- Comorbidities included in the Charlson Comorbidity Index
- ICS history (yes/no)
- ICS history duration
- Season of index date
- Index year
- Baseline all-cause resource use (presence vs. absences of hospitalizations, or ER visits, or outpatient visits)
- Baseline other asthma medications (use vs. no use)

Proprietary confidential information © 2021 Boehringer Ingelheim International GmbH or one or more of its affiliated companies

- Baseline overall medication history (polypharmacy defined as number of unique medications)
- Insurance type
- Hypertension
- Gastroesophageal reflux disease
- Allergic Rhinitis
- Obesity
- Sinusitis
- Obstructive sleep apnea
- Cardiovascular disease
- Diabetes
- Renal failure
- Arthritis
- Osteoporosis
- Depression
- Cancer (excluding basal cell carcinoma)
- Baseline pneumonia diagnosis
- Baseline acute bronchitis diagnosis
- Diagnosis of dyspnea during baseline identified using ICD 9 786.0x and ICD 10 R06.0x
- Diagnosis of alcohol dependence during baseline identified using ICD 9 303.xx, 305.0x and ICD 10 F10.xx
- Smoking dependence during baseline identified using ICD 9 305.1 and ICD 10 F17.xx

In addition to the key independent variable of interest (ICS+TIO vs ICS/LABA group), we will include time varying medication exposure as a covariate in the regression.

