9.5 STUDY SIZE

There are 25,291 patients with a prescription claim for tiotropium (1.25mcg, October 2015-May 2020) identified for analysis and 1,125,657 patients with ICS/LABA prescription claims (July 2014-May 2020). After excluding patients with COPD there are 17,882 patients in the Tio group and 921,804 patients in the ICS/LABA group. Further inclusion-exclusion criteria as well as restricting the Tio group to those with concurrent ICS monotherapy, will be applied to arrive at the final sample.

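### Patients with exactly one COPD code stay in the cohort, and no COPD indicator is matched on or checked for balance

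*Combined protocol and SAP*

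**What the plan says.** Section 9.1 requires repeated asthma coding for entry ("Patients with least two asthma diagnosis (ICD 9 CM: 493.xx or ICD 10: J45-J45.999) will be included") and applies the same two-code threshold to COPD for exclusion: "Patients with least two diagnosis of COPD at any time during the study period will be excluded". The treatment groups are defined by "Patients will be required to be concurrently on ICS+Tiotropium (specifically Tiotropium Respimat® 1.25 mcg) or ICS/LABA".

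Section 9.5 gives the counts before and after the COPD step: "There are 25,291 patients with a prescription claim for tiotropium (1.25mcg, October 2015-May 2020) identified for analysis and 1,125,657 patients with ICS/LABA prescription claims", then "After excluding patients with COPD there are 17,882 patients in the Tio group and 921,804 patients in the ICS/LABA group". It adds that the other eligibility criteria, and the restriction of the tiotropium group to concurrent ICS monotherapy, are still to be applied.

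COPD is not a separate item in Table 1 or in 9.3.3. The nearest entry is the Charlson index, which Table 1 gives as "Charlson Comorbidity Index score" and 9.3.3 gives as "Comorbidities included in the Charlson Comorbidity Index". Neither place lists components or codes. Matched variables that are partly related to COPD are age group, smoking dependence, dyspnea, pneumonia and acute bronchitis.

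The only sensitivity analyses planned in 9.1 vary the exposure window (0% and 100% additional days). The limitations in 9.9 mention patient misclassification in general but not COPD overlap.

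**The concern.** By making COPD an exclusion, the plan treats it as a condition that does not belong in this comparison. The two-code rule leaves some patients with a recorded COPD diagnosis in the cohort. If they are more frequent in one arm and have a different event rate, the comparison is confounded.

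The planned safeguards act only on listed variables. The p-value check, the SMD limit of 0.1 and the decision rule for differences that remain after matching cannot respond to an indicator that is not tabulated. A matched total Charlson score does not ensure balance on any one component. If the index has a pulmonary item that also counts asthma, that item is constant in a cohort where everyone has coded asthma, and it gives no control. Only a separately coded COPD item would help, and the plan does not say there is one.

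The estimates at stake are the primary hazard ratio and the secondary results on corticosteroid use and resource use. Section 7 summarises the randomized trials as showing similar responses in the two regimens, so a shift of a few percent in a hazard ratio could matter to the interpretation.

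**Working it through.** **Inputs from the plan (9.5).** Tiotropium: 25,291 before and 17,882 after the COPD exclusion. ICS/LABA: 1,125,657 before and 921,804 after. The plan states these as raw counts, with no power or effect-size figure to reproduce.

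**Step 1: share removed for COPD.**
- Tiotropium: 25,291 − 17,882 = 7,409; 7,409/25,291 = 29.3%.
- ICS/LABA: 1,125,657 − 921,804 = 203,853; 203,853/1,125,657 = 18.1%.
- Difference 11.2 percentage points (95% CI 10.6 to 11.8); ratio 1.62.

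The ICS/LABA claims window is the longer one (from July 2014, against October 2015), so a shorter window does not explain its lower share.

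**Step 2: assumptions.** The documents do not give the prevalence of single-code COPD or its effect on exacerbation. Assumed: prevalence p0 in ICS/LABA of 3% or 5%; p1 = 1.62 × p0 in ICS+Tio, carrying over the ratio from Step 1; risk ratio h of 1.5, 2 or 3 for single-code patients against the rest.

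**Step 3: imbalance before matching.** SMD = (p1 − p0)/√{[p1(1 − p1) + p0(1 − p0)]/2}.
- p0 = 3%, p1 = 4.85%: SMD = 0.096.
- p0 = 5%, p1 = 8.09%: SMD = 0.125.

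The plan's limit of 0.1 is therefore reached at a little above 3%.

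**Step 4: bias factor on the hazard ratio before matching.** Factor = [1 + p1(h − 1)]/[1 + p0(h − 1)].

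| p0 | p1 | h = 1.5 | h = 2 | h = 3 |
|---|---|---|---|---|
| 3% | 4.85% | 1.009 | 1.018 | 1.035 |
| 5% | 8.09% | 1.015 | 1.029 | 1.056 |

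For example, at p0 = 5% and h = 2: 1.0809/1.05 = 1.029. Over a wider range of prevalence at the same group ratio, the factor is 1.003-1.012 at p0 = 1% and 1.03-1.10 at p0 = 10%.

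**Step 5: direction on the primary endpoint.** Section 9.3.2.1 counts only hospitalizations and ER visits with asthma as primary diagnosis. If some events in single-code patients are coded to COPD, those patients may show fewer counted events. With an assumed h = 0.7 the factor is 0.994 at p0 = 3% and 0.991 at p0 = 5%, which favours ICS+Tio. The corticosteroid component in 9.3.2.2 and all-cause resource use need no asthma diagnosis, so this mechanism does not apply to them.

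**Step 6: with the indicator balanced.** Then p1 = p0 and the factor is 1.00 for this confounder.

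**The case against.** The two-code rule is a defensible choice. It mirrors the two-code asthma rule and searches the whole study period, so a patient with one code before index and another at any later time is already removed. Those who remain never had the diagnosis repeated in the available data, and some may not have COPD. This limits the number affected. It does not show that they are evenly spread between arms.

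The 29.3% and 18.1% do not describe the study arms. They precede the ICS restriction, the other criteria and matching, and the tiotropium count may still include patients who take it with ICS/LABA. Section 9.5 does not restate the two-code rule, and part of the gap may reflect age, which is matched. This stands: the counts suggest channelling but do not measure the residual imbalance.

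The matched proxies will also remove part of any imbalance. That stands too, but the plan has no way to show how much remains.

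A reader might infer three stronger points that the documents do not support:
- **That the Charlson index certainly gives no control.** Its components are not stated, so this is open.
- **That the result must be biased against ICS+Tio.** On the primary endpoint the direction depends on how events in these patients are coded.
- **That the bias is large.** An assumed 15% against 5% with a risk ratio of 3 gives (1 + 0.15 × 2)/(1 + 0.05 × 2) = 1.18, but that needs a group ratio of 3, well above the 1.62 in the plan's own counts.

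**Conclusion.** The gap is real and its likely effect is modest. Single-code COPD patients are retained, no separate indicator is matched or tabulated, and no planned analysis tests the COPD rule.

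If the crude ratio of 1.62 carries over, with 3-5% prevalence in ICS/LABA and a risk ratio of 1.5-3, the factor on the hazard ratio is about 1.01-1.06 before matching and smaller after it. At a risk ratio of 2 it is about 2-3%. The prevalence, the risk ratio and the carry-over of the ratio are all assumptions. Bias against ICS+Tio is more plausible for corticosteroid use and all-cause resource use; on the primary endpoint the sign is not determined. That uncertainty is itself a reason to measure the variable. The change should be made before analysis, but the point does not invalidate the design.

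**What to change.** 1. Add a yes/no variable for any COPD code before index to Table 1 and 9.3.3, include it in the propensity score, and report its SMD before and after matching. Since criterion 3 removes patients with two or more codes, it will mark those with exactly one, recorded before index. State the look-back period and use the same one in both arms. Codes first recorded after index should not enter this variable.
2. Add one sensitivity analysis of the primary endpoint that excludes patients with any pre-index COPD code.
3. List the Charlson components and codes, and say whether the score or the individual comorbidities enter the propensity score, since Table 1 and 9.3.3 differ.

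The cost is one extra variable, from codes already needed for criterion 3, and one extra model run. The sensitivity analysis will lose some ICS+Tio patients and so some precision.
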